**C.12. Sample Size, Power Analyses (RQ-2, RQ-4, IR-3).** The revised sample size estimate of 115 per group for analyses is based on ensuring adequate power for Aim 1 (see Table 4). The main objective is to compare the 12-month CRC screening rates with any test among the three groups, so the binary outcome of any CRC screening test completion at 12 months as documented in the electronic medical record has driven calculation of our sample size. For Aim 1, we will first test whether there is any overall group difference in CRC screening completion rates using a chi-square test at 5% significance level. If a significant difference is observed, pairwise comparisons will be conducted at  $\alpha=1.7\%$  (5%/3 pairwise tests) to account for multiple testing. Expected CRC screening rates, based on prior studies demonstrating the effects of computer-tailored and PN interventions, are shown in Tables 1 and 2, respectively. We have revised our DVD only effect calculations from the original estimate of 15.5% to 20% for this group. We originally proposed a DVD only effect size of 15.5% based upon the average effect size of studies listed in Table 1. This 15.5% estimate assumed that the lowest rate observed in the DVD only group might be near 20% ([name], 2015) and lowered that rate even further to 15.5% to be more conservative, as statisticians typically assume very conservative effects when doing power calculations. However, by assuming a value closer to, but still less than the lowest rate observed in the literature for a comparable population (which was 22% seen in [name], 2015 per Table 1), the samples sizes can be reduced to 115 per group for Aim 1. This sample size will afford at least 80% power for all three comparisons per Table 4 below. To allow for an approximate 25% attrition which the project is experiencing as of May 31, 2019 and still have 115 per group for analyses, a total sample size of 450 enrolled subjects is required.

**Table 4. Revising the expected rate in the DVD group to 20% (still smaller than the smallest rate for a tailored intervention in Table 1)**

Comparison	Rates	Sample Size for Groups	Power
PN+DVD vs DVD only	44% vs 20%	115 vs 115	92%
PN+DVD vs Usual Care	44% vs 5%	115 vs 115	99%
DVD only vs Usual Care	20% vs 5%	115 vs 115	80%

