Several studies have shown that patient navigation is an effective method to increase CRC screening rates especially in minority groups with effect sizes shown in Table 2 (average of 33.7). We conservatively estimated a 44% (less than 33.7 + 20 = 54%) effect size for the PN + DVD since we will enroll patients who have previously canceled a screening colonoscopy appointment. For usual care, we used the estimate from [name], 2015 in Table 1 as it is most similar to the proposed study. See Table 5 below for summary. At 12 months, 115 in each group will yield at least 80% power for detecting the pair-wise differences (44% v. 20% v. 5%) in completion rates among the three groups using pair-wise chi-square tests or bivariate logistic regression models and a two-sided  $\alpha=.017$  level. Back-calculation, assuming an attrition rate that is approximately 25% from the sample size needed at 12 months, it requires that we approach 600 eligible subjects to enroll 450 (75% participation rate) and randomly assign them to the three intervention groups (150 per

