**Table 5. Power Analyses**

Time/Test	PN plus DVD (n=115 at 9 mos)	DVD only (n=115 at 9 mos)	Usual Care (n=115 at 9 mos)	Power
9 month/ Any Test	44%	20%	5%	.80-.99

group). By 12 months, the 150 in each intervention group will decrease to 115 through an approximate 25% attrition. The multivariable logistic regression models for the intervention effect on the CRC screening completion outcome while accounting for covariates will very likely have greater than 80% power, more than for the bivariate models because a smaller sample size is required when

covariates are added to the model. In addition, this sample size will most likely ensure greater than 80% power for other outcomes of Aim 1 (quality of bowel preparation, anxiety, and satisfaction) because they are continuous or ordinal variables. Specifically, the analysis of continuous outcomes using a general linear model will have 99% power to detect a

small effect size of .50 standard deviation units between outcome means, and the ordinal logistic regression models will have more information than the binary models.

For Aim 2, our main interest is in whether the intervention effects differ by age, race, gender, and income. We consider this aim to be exploratory as we do not have preliminary data to estimate the effect sizes; however, we feel it is important to explore interactions in this study as they may identify subgroups of patients who may not need the more intensive support of a PN. For Aim 3, the revised sample size of 115 per group will allow for the detection of mediation effects with 80% power assuming the effect sizes from the intervention to mediator and from the mediator to outcome are moderate or higher (which is what is typically assumed in a power calculation). For Aim 3, to test mediation effects, we will use the percentile bootstrap method to estimate the indirect/mediated effect. Simulations of the two-path mediation model in Mplus (Table 2) show that 115 subjects per group are needed to have 80% power to test the total indirect effect using the Sobel approach when the effect of the independent variable (the intervention variable here) on the mediator is small (.2) and independent variable on outcome is medium (.39). Using the percentile bootstrap method instead of Sobel should afford the same or greater power.

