## E. Patient Population (RQ-2, RQ-3, RQ-4, PC-1, PC-2)

**E.1. Sample and eligibility criteria.** 450 people who canceled or did not attend their colonoscopy appointment will be enrolled in this study. Participants will be eligible if they are 50-75 years old if non-African American or 45-75 years old if African American and were referred to Eskenazi's endoscopy unit for a colonoscopy. Stratified block random assignment to each of three groups will be performed within 12 strata formed by crossing sex, three race/ethnicity groups, and two age levels (male/female, Black/White/Hispanic, age<65/age 65+) to ensure that the three randomized groups are comparable in distribution of sex, race/ethnicity, and age. At the completion of the baseline interview, patients will be randomly assigned to the tailored DVD-only group, the tailored DVD plus patient navigator group, or usual care. Based on the 65% participation rate we achieved in our recent R01 conducted in this same health system, we conservatively estimated our participation rate at 55%. However, our actual, cumulative participation rate for eligible subjects was 75% through May 31, 2019. Therefore, we will need to contact approximately 600 eligible people to enroll 450. Data from 2014

indicate the availability of 1150 potentially eligible patients during that 12 month period (See Table 6). An estimated 2200 would be available over the 24 month enrollment period. Based on our preliminary studies, no more than 20% attrition was anticipated at 9 months. Actual data from Year 3 of this project as of May 31, 2019 shows an attrition rate closer to 25% at the 6 month follow-up timepoint. This approximate 25% rate is being used in re-calculating the sample size required.

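### Section C.12 claims 99% power for a 0.50 SD difference with 115 per group; a two-sided, unadjusted two-arm comparison gives 96.5% at .05 and 91.6% at .017, and the figure does not carry over to satisfaction or H1.3

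*Combined protocol and SAP*

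**What the plan says.** Section C.12 sizes the trial on 12-month screening completion and arrives at "The revised sample size estimate of 115 per group for analyses". Enrolment is 450, equally allocated, and "By 12 months, the 150 in each intervention group will decrease to 115 through an approximate 25% attrition".

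After the binary calculation, C.12 turns to the remaining Aim 1 outcomes and says "this sample size will most likely ensure greater than 80% power for other outcomes of Aim 1", naming bowel preparation quality, anxiety and satisfaction. It then becomes specific: "the analysis of continuous outcomes using a general linear model will have 99% power to detect a" given difference, which it goes on to describe as a "small effect size of .50 standard deviation units between outcome means". That sentence has no alpha, no sidedness and no contrast.

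Three other places bear on it:

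- **Alpha.** The two-sided .017 level (.05/3) in C.12 and C.13 is attached to pairwise tests of screening completion. For anxiety and satisfaction, C.13 specifies only linear regression.
- **Contrast.** C.13 codes group by dummy variables with usual care as reference. It spells out H1.2, which is worded in terms of either intervention, as two separate comparisons of one arm with usual care.
- **Population.** H1.3 (section C) concerns participants who complete colonoscopy. Section C.8 asks about satisfaction with screening only among those who were screened.

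**The concern.** A power of 99% for half a standard deviation looks too high for 115 per arm, and the sentence does not give enough to reproduce it. The natural reading is pairwise: Table 4 compares 115 with 115, and the text just before Table 5 says "At 12 months, 115 in each group will yield at least 80% power for detecting the pair-wise differences".

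The practical risk is in how a null result is read. As printed, a null finding for anxiety or satisfaction could be taken to exclude a difference of 0.50 SD with a 1% chance of having missed it. The size label adds to this, because a reader may conclude that small differences are covered as well. The sentence also applies the 115 to outcomes that will not be observed, or under H1.3 not analysed, in 115 people per arm.

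**Working it through.** **Inputs.** d = 0.50 SD, 115 analysed per arm, 150 enrolled per arm, and the .017 and .05 levels (C.12, C.13); planned screening rates of 44%, 20% and 5% (Table 4).

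**Formula.** λ = d / √(1/n₁ + 1/n₂). The normal approximation to two-sided power is Φ(λ − z₁₋α/₂). The figures relied on use the non-central t with n₁ + n₂ − 2 degrees of freedom.

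**1. Trying to reproduce 99% at 115 against 115.** λ = 0.5/√(2/115) = 3.791.

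- Two-sided .05: Φ(3.791 − 1.960) = 0.9665; non-central t **96.5%**.
- Two-sided .017: Φ(3.791 − 2.387) = 0.9199; non-central t **91.6%**.

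Neither gives 99%.

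**2. Number per arm for 99%, pairwise.** n = 2(z₁₋α/₂ + 2.326)²/d².

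- .05: 8 × (1.960 + 2.326)² = 147.0; 148 by non-central t.
- .017: 8 × (2.387 + 2.326)² = 177.7, so 178; 180 by non-central t.

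**3. Settings that come closer.**

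| Setting | Power for 0.50 SD |
|---|---|
| 150 vs 150, two-sided .05 | 99.1% |
| 150 vs 150, two-sided .017 | 97.3% |
| Both interventions pooled vs usual care, 230 vs 115, two-sided .05 | 99.2% |
| Same pooled contrast, .017 | 97.6% |
| 115 vs 115, one-sided .05 | 98.4% |
| Three-arm F test, 115 per arm, .05, means 0, 0.25, 0.5 | 93.2% |
| Three-arm F test, 115 per arm, .05, one arm 0.5 away from the other two | about 98% |

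For the pooled contrast, λ = 0.5/√(1/230 + 1/115) = 4.378.

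**4. The size label.** For 0.20 SD with 115 per arm, power is 33% at .05 and 19% at .017.

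**5. Colonoscopy completers (H1.3).** The plan gives no expected number. As an upper bound under its own rates, assume every screener among the 115 has a colonoscopy: 0.44 × 115 = 50.6, 0.20 × 115 = 23, 0.05 × 115 = 5.75, or about 51, 23 and 6. For 51 vs 6, λ = 0.5/√(1/51 + 1/6) = 1.16.

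| Contrast with usual care | .05 | .017 |
|---|---|---|
| DVD + navigation, 51 vs 6 | 20.6% | 10.4% |
| DVD only, 23 vs 6 | 18.2% | 8.8% |
| Both pooled, 74 vs 6 | 21.3% | 10.9% |

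**The case against.** **The printed figure can be reached at 115 per arm.** H1.3 speaks of either intervention; read as a pooled contrast, 230 against 115 gives 99.2% at two-sided .05. This stands as arithmetic. A reader might infer that the authors must have used the 150 enrolled at an uncorrected .05, but the documents show no derivation and more than one route leads to 99%, so that inference is unsupported. The pooled contrast is itself stated nowhere, and the way C.13 spells out H1.2 points to separate arm comparisons.

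**The .017 level was never assigned to these outcomes.** This stands. The documents do not establish that the chance of missing 0.50 SD is 8% rather than 1%; that is what follows if .017 is extended. At .05 the chance is 3.5%.

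**A general linear model may carry covariates.** C.13 provides for adjustment, and Table 3 includes baseline anxiety. Covariates correlating about 0.47 with the outcome would restore 99% at .05 (about 0.60 at .017). The plan states no such correlation, so this cannot support the 99%, but it is why the recomputed figures must be labelled unadjusted.

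**Attrition.** Section E.1 "shows an attrition rate closer to 25% at the 6 month follow-up timepoint", and a reader might infer that fewer than 115 will remain at 9 months. Section C.14 puts the loss at about 25% over the whole 9 months, and C.8 (retention) tells people who miss the 6-month interview that they can stay in the study. Continuing loss would be an assumption, and nothing here uses it.

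**The size label.** The .2 and .39 that C.12 uses for mediation are effects in a path model, not mean differences in SD units, so they do not show the label to be inconsistent.

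**Nothing rests on the claim.** Sample size was set by the binary outcome, and the broader claim for these outcomes is power above 80%. Both pairwise figures at 115 per arm meet that. It fails only for H1.3 under the step 5 assumption.

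**Conclusion.** The 99% is not what a two-sided, unadjusted comparison of 115 with 115 delivers. It overstates power by about 2.5 points at .05 and 7.4 points at .017, the latter resting on an extension of the screening level. Because alpha, sidedness and contrast are missing, the figure cannot be verified as printed. The shortfall alone is modest and does not undermine the trial's size.

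The recomputed figures are no general replacement. They hold only for outcomes measured in all interviewed participants, with 115 per arm analysed. They do not describe satisfaction (screening completers) or H1.3 (colonoscopy completers). For H1.3, under the plan's own rates and the generous assumption that every screener has a colonoscopy, power for 0.50 SD is about 21% at .05 for 51 against 6, and pooling the interventions does not change that materially. This part rests on an assumed split of tests; any use of FIT among screeners lowers the completer counts.

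**What to change.** In C.12:

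1. Replace the 99% statement with: *about 97% power at two-sided .05 (92% at .017) for a pairwise 0.50 SD difference with 115 analysed per arm, unadjusted.* State which alpha and which contrast the analysis will use.
2. Drop the word small.
3. Add that this figure applies only to outcomes measured in all interviewed participants, and not to satisfaction or H1.3.
4. For H1.3, restate power from the expected number of colonoscopy completers per arm, with the assumed share of screeners choosing colonoscopy. If no better estimate exists, give the upper bound above: about 51, 23 and 6, with about 21% power at .05 for 51 against 6.

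The cost is a few sentences and a less favourable stated power. Enrolment, data collection and the analyses do not change.

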For Aim 1, we will test the primary hypothesis related to comparing intervention effects among the three randomized groups (H1.1: PN+DVD vs. DVD only and H1.2: PN+DVD vs. usual care and DVD only vs. usual care) using the outcome of completion of CRC screening using any test at 12 months post-baseline. In addition, quality of bowel preparation, procedural anxiety, and satisfaction with the screening experience will be examined as outcomes. As an initial assessment of CRC screening completion at 12 months, we will use a chi-square test for a 3 x 2 (group by screening completion) contingency table to test whether completion rates differ across groups. If the  $p$ -value for the overall test is significant at the .05 level, pair-wise 2 x 2 tests will be conducted at the  $.05/3 = .017$  level. However, the primary analyses for Aim 1 will involve fitting multivariable logistic regression models of the primary outcome of 12-month CRC screening test completion (yes/no). Independent variables will be group assignment and continuous and categorical individual characteristics. These models will also allow us to investigate intervention effects on CRC screening test completion while adjusting for potential confounders. Group assignment will be coded using dummy variables with usual care as the reference category. For H1.3, quality of bowel preparation will be analyzed for those participants who complete colonoscopy with proportional-odds ordinal logistic regression using an ordinal dependent variable ( $1 = \text{excellent}$ ,  $2 = \text{good}$ ,  $3 = \text{fair}$ ,  $4 = \text{poor}$ ,  $5 = \text{inadequate}$ ). If some outcome categories are sparse, the outcome will be dichotomized into adequate

(*excellent or good*) versus inadequate (*fair, poor, or inadequate*). The outcomes of anxiety and satisfaction are continuous outcomes and will be modeled with linear regression.

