**Aim 2. Examine age, race/ethnicity, sex and income as potential moderators of intervention effects. (RQ-4, HT-1, HT-2, HT-3, HT-4)** We will fit multivariable models as in Aim 1, except now including interaction terms for age (< 65, age 65+), race/ethnicity (Non-hispanic Black, Non-hispanic White), sex (male, female), and annual income (<\$15,000, ≥\$15,000), respectively. Moderators will be identified by significant interaction terms in regression models. The key moderation effects of interest will be between PN+DVD vs. DVD only. Moderation of PN+DVD vs. usual care, and DVD only vs. usual care also will be examined. Hispanics will be excluded from race/ethnicity interaction tests due to small sample sizes.

**Aim 3. Examine changes in knowledge and health beliefs (knowledge, perceived risk, perceived benefits, barriers, and self-efficacy) as potential mediators of intervention effects. (RQ-6)** Mediation analysis will be conducted to identify potential mediators. Specifically, for each of the variables (changes in knowledge, perceived risk, perceived benefits, perceived barriers, and self-efficacy) mediation effects will be estimated in an logistic regression setting, fitting the appropriate mediation models using MPlus and then testing indirect effects using the percentile bootstrap approach to estimate the indirect effect. We will fit models that estimate the effects of PN plus DVD vs usual care and DVD only vs usual care, and also models that compare the strength of the indirect effects between the PN plus DVD and DVD only arms. We expect to see a difference in mediation effects mainly on barriers, with the PN plus DVD having a greater mediation effect on barriers than DVD only.

**C.14. Potential problems, strategies and benchmarks for success.** Potential problems are described below along with plans to minimize them. (*IR-6, MD-1, MD-2, MD-4*)

- *Loss to follow-up:* It is anticipated that there will be some loss to follow-up because of participant dropout, death, or relocation. Based attrition data through May 31,2019 , we estimate the loss to be approximately 25% over the 9-month study period, which has been accounted for in the revised power analysis and sample size determination.
- *Limited internal validity:* Randomization will minimize the influence of extraneous variables on outcomes.

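### Aim 2 looks for patients who may not need a navigator, but for screening completion it plans only odds-ratio interactions and no absolute gains by subgroup

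*Combined protocol and SAP*

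**What the plan says.** C.12 gives the purpose of Aim 2: interactions are worth exploring because "they may identify subgroups of patients who may not need the more intensive support of a PN". Section E of Protection of Human Subjects adds that knowing which subgroups respond to the DVD alone, and which need more intensive help, would let the team target its efforts better. C.12 also limits the aim: "We consider this aim to be exploratory as we do not have preliminary data to estimate the effect sizes".

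The method is in C.13. Under Aim 1, twelve-month screening completion is modelled by multivariable logistic regression. Under Aim 2, the Aim 1 models are refitted with interaction terms for age, race/ethnicity, sex and income. The rule is "Moderators will be identified by significant interaction terms in regression models", and on the contrasts it says "The key moderation effects of interest will be between PN+DVD vs. DVD only"; the two contrasts with usual care are examined as well.

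The documents do not name the scale of the interaction; it follows from the logistic model. They do not plan screening rates by arm and subgroup, risk differences by subgroup, or an interaction on the additive scale.

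**The concern.** The coefficient of a group-by-subgroup term in a logistic model is the log of a ratio of odds ratios. It is zero when the odds ratio for navigation is the same in both subgroups, whatever the number of extra people screened. If the subgroups have different screening rates under the DVD alone, one odds ratio corresponds to different absolute gains, and one absolute gain corresponds to different odds ratios.

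A team deciding where to spend navigator time would want to know how many more people are screened per 100 navigated in each subgroup. The planned rule yields only a verdict of moderator or no moderator and never produces that figure. A finding of no moderation could be read as equal benefit when the gains differ, and a significant term could be read as unequal benefit when the gains are the same.

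**Working it through.** **Inputs.** Table 4 (C.12) expects 44% screened with PN+DVD and 20% with DVD only, with 115 analysed per group. C.12 enrols 150 per group, and C.13 takes this outcome from the medical record even for dropouts, so between 115 and 150 per arm may be available. The Aim 1 pairwise level is 0.05/3, two-sided. No level is stated for Aim 2; I assume 0.05 two-sided, two subgroups of equal size and no other covariates. Subgroup DVD-only rates are my assumptions throughout.

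**The plan's own figure.** With d the difference in rates, SE0 the pooled and SE1 the unpooled standard error, and a continuity correction, power = Φ((d − 1/n − 2.394 × SE0)/SE1). For 44% vs 20%, SE0 = 0.0615 and SE1 = 0.0594, so (0.24 − 0.0087 − 0.1473)/0.0594 = 1.41 and power is 92.1%, against 92% in Table 4. The same formula gives 80.8% for 20% vs 5% (stated 80%). The planning rates are therefore taken as they stand.

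**Planned effect on both scales.** The risk difference is 44 − 20 = 24 points. OR = (0.44/0.56)/(0.20/0.80) = 3.14.

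**Same odds ratio, different gains.** With DVD-only rate p and odds o = p/(1 − p), the PN+DVD rate is 3.143 × o/(1 + 3.143 × o).

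| DVD only (assumed) | PN+DVD | Gain (points) | Navigated per extra person screened |
|---|---|---|---|
| 10% | 25.9% | 15.9 | 6.3 |
| 19% | 42.4% | 23.4 | 4.3 |
| 20% | 44.0% | 24.0 | 4.2 |
| 21% | 45.5% | 24.5 | 4.1 |
| 30% | 57.4% | 27.4 | 3.7 |
| 40% | 67.7% | 27.7 | 3.6 |

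The logistic interaction between any two rows is exactly zero. The gain differs by 24.5 − 23.4 = 1.1 points for 19% vs 21%, and by 27.4 − 15.9 = 11.5 points for 10% vs 30%.

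**Same gain, different odds ratios.** Adding 24 points to 10% and to 30% gives (0.34/0.66)/(0.10/0.90) = 4.64 and (0.54/0.46)/(0.30/0.70) = 2.74, a ratio of 0.59. A Wald test of that ratio would be significant in about 13% of trials at 115 per arm and 15% at 150, against a nominal 5%.

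**What a risk-difference analysis could show.** In the 10%/30% example with constant odds ratio, the variance of the difference in risk differences is the sum of p(1 − p)/n over the four cells, which is 0.736/n.

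- At 115 per arm (57.5 per cell), SE = 11.3 points, 11.5/11.3 = 1.02, and power is about 17%.
- At 150 per arm (75 per cell), SE = 9.9 points, 11.5/9.9 = 1.16, and power is about 21%.
- In the equal-gain example the SEs are 11.6 and 10.2 points. Across both examples, 95% half-widths (1.96 × SE) are about 19 to 23 points.
- For 80% power in the first example, the gains would have to differ by about 2.80 × 9.9 = 28 to 2.80 × 11.3 = 32 points.

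**The case against.** Several objections have force.

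- **The documents do not define need as extra people screened per 100 navigated.** They also speak of who responds to the DVD alone and, in section B, of reaching those least likely to be screened. In the 10%/30% example a rule based only on risk differences would rank the worse-screened subgroup as gaining less. This stands: the risk difference should not be the sole criterion, and subgroup rates must be read with it.
- **The scales agree in the strict case.** A subgroup that gains nothing has an odds ratio of 1 and a risk difference of 0. If another subgroup benefits, there is interaction on both scales. This stands.
- **The gap may be small.** Table 6 shows colonoscopy completion of 40.3% vs 42.2% for Black and White patients and 40.2% vs 42.1% for men and women, about 2 points each. A 2-point gap around 20% moves the gain by about 1 point. This stands for the key contrast, with the limit that Table 6 covers one test among all patients with orders. Nothing is given by age or income.
- **The aim is exploratory, and low power dominates on any scale.** This stands too. It argues for estimates with intervals rather than for a second significance test.

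A reader might infer that the planned rule will miss or invent moderators. The documents do not support this: they do not show that subgroup rates differ enough, and a difference in odds ratios is real on its own scale. Nor does the general provision in C.13 for sensitivity analysis as needed close the gap. It concerns model assumptions and names no effect scale.

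**Conclusion.** The point holds in limited form. For screening completion, Aim 2 judges moderation only through the significance of a ratio of odds ratios and never produces the absolute gain from navigation by subgroup, although its stated purpose is to find patients who may not need a navigator.

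The consequence depends on unknown rates. At a constant odds ratio of 3.14 it runs from about 1 point (DVD-only 19% vs 21%) to 11.5 points (10% vs 30%). These figures assume equal subgroups and no covariates.

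A reader might also infer that a risk-difference test should replace the planned one and would settle who needs navigation. It would not: in the 10%/30% example it would miss the difference about four times in five. A non-significant interaction on either scale cannot show that a subgroup can do without a navigator.

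This is a cheap improvement to an exploratory aim. The Aim 1 comparison is untouched, and the linear models for anxiety and satisfaction are not affected.

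**What to change.** For screening completion, add to C.13, Aim 2:

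- From the same logistic models, report standardised screening rates by arm and subgroup.
- Report the risk difference for PN+DVD vs DVD only in each subgroup, and the difference in risk differences, with 95% confidence intervals by the delta method or bootstrap.
- Show these beside the odds-ratio interaction, which stays.
- Base any statement on who may not need navigation on these estimates and intervals together with the subgroup rates, not on the significance of an interaction term on either scale.
- State that power is low on both scales and that the results are exploratory.

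The cost is a short SAP text, a post-estimation step and one extra column per moderator. The intervals will be wide. No new data, participants or changes in conduct are needed.

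### The 80% power stated for Aim 3 is not established for the planned logistic mediation analysis

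*Combined protocol and SAP*

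**What the plan says.** In section C.12, in the text following Table 5, the plan states that "the revised sample size of 115 per group will allow for the detection of mediation effects with 80% power". The condition it attaches concerns both links in the chain: "effect sizes from the intervention to mediator and from the mediator to outcome are moderate or higher". No numbers accompany that sentence.

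The paragraph then cites an Mplus simulation. It says that "115 subjects per group are needed to have 80% power to test the total indirect effect using the Sobel approach". The inputs behind that figure are that the intervention's influence "on the mediator is small (.2) and independent variable on outcome is medium (.39"). It adds that the percentile bootstrap should do at least as well as the Sobel test.

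In section C.13, Aim 3, "mediation effects will be estimated in an logistic regression setting", with indirect effects tested by percentile bootstrap. The contrasts are each intervention arm against usual care, plus a comparison of indirect effects between the two intervention arms. The screening outcome is yes/no, with assumed rates of 44%, 20% and 5% (C.12).

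C.12 calls Aim 2 exploratory. It does not say so of Aim 3.

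**The concern.** Four things stand between the stated 80% and the analysis that will be run.

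- The same path, intervention to mediator, is described as moderate or higher and then as small (.2).
- An indirect effect is the product of intervention-to-mediator and mediator-to-outcome. The second figure given, .39, is worded as intervention to outcome, so the mediator-to-outcome value is missing.
- Nothing says whether .2 is a difference between arms in SD or a standardised coefficient. With two equal arms these differ by a factor of about two. The labels do not settle it, since the same section also calls .50 SD small. No alpha is given for Aim 3.
- The planned model has a binary outcome. The cited simulation is described only as a two-path model, with no outcome type stated.

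At stake is how far the mediation results can be relied on. Aim 3 is presented as powered, so a reader may give a non-significant mediator more weight than the design supports.

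**Working it through.** **Inputs.** 115 per arm, so 230 per pairwise contrast (C.12); .2 and .39 (C.12); screening rates of 5/20/44% (C.12). Assumed: two-sided .05, and .39 taken as the mediator-to-outcome effect because no other value is given. Each figure is for one mediator in one pairwise contrast.

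**1. Two readings of .2.** As an SD difference, d = 0.2. As a standardised coefficient with equal arms, d = 2(.2)/√(1 − .2²) = 0.4/0.980 = 0.408, or 0.4 with ±1 coding and unit residual SD.

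**2. Reproducing the plan's 80%.** The Sobel statistic is z = ab/√(a²·s_b² + b²·s_a²), where a is intervention to mediator and b is mediator to outcome. Simulated power with a continuous outcome, N = 230 and b = .39:

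- .2 as an SD difference: 28%
- .2 as a standardised coefficient: 82.5% (84.4% fully standardised)
- .39 SD between arms as the a-path, with b = .39: 80.2%

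The stated figure is therefore approached with a continuous outcome on the second and third readings. That the cited simulation used a continuous outcome is an inference from this result; the plan does not say so.

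If .39 is instead taken literally as intervention to outcome and b is left open between .14 and .59, Sobel power runs from 5% to 31% (SD reading) or 28% to 85% (standardised reading). At alpha .017, the 82.5% falls to 65%.

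**3. Ceiling from the first path.** At d = 0.2 the arm-to-mediator test has non-centrality 0.2 × √(115/2) = 1.52. Its power is about P(Z > 1.96 − 1.52) = 33%. The indirect effect cannot do materially better, whatever b is. For 80% on that path alone, n = 2(1.96 + 0.84)²/0.2², which is 393 per arm.

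**4. The planned binary outcome.** Linear mediator model, logistic outcome model, 115 per arm. Ranges are over the three pairs of arms. The .39 is taken either as log-odds per mediator SD, or as a latent-scale slope: .39 × π/√3 = .71 log-odds.

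| Arm to mediator | Mediator to outcome (log-odds per SD) | Sobel | Joint significance | Percentile bootstrap |
|---|---|---|---|---|
| 0.2 SD | .39 | 3-8% | 14-23% | 12-24% |
| 0.2 SD | .71 | 14-24% | 30-34% | 29-33% |
| 0.41 SD | .39 | 20-39% | 40-64% | 39-69% |
| 0.41 SD | .71 | 61-77% | 80-86% | 84-89% |
| 0.5 SD | .39 | 28-53% | 44-69% | not run |
| 0.5 SD | .71 | 74-92% | 87-96% | not run |

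The bootstrap column rests on 300 simulated trials per setting, so its Monte Carlo standard error is up to √(.5 × .5/300) = 2.9 points. A second set of simulations (360 trials per setting, 0.4 SD for the standardised reading, .66 log-odds for the latent slope) gave bootstrap power of 14-24% and 29-34% at 0.2 SD, and 39-66% and 74-86% at 0.4 SD. Joint significance serves as a proxy for the bootstrap in the 0.5 SD rows.

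**5. Attrition.** The 6-month interview measures the change in the mediators (Table 3). At the roughly 25% attrition reported for that visit (E.1), 150 × 0.75 = 112.5 per arm, slightly below 115.

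**The case against.** The best defence is that the statement is under-specified, not wrong.

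- The scale of .2 and .39 and the outcome type would be in the cited methods paper. The table reference in that sentence appears to point there, since the plan's own Table 2 lists navigation trials.
- A .39 SD difference between equal arms is a standardised path of .39/√(.39² + 4) = .19. A moderate .39 SD and a small standardised .2 may therefore be nearly the same scenario under different labels.
- On the standardised reading with a latent-scale .39, the planned bootstrap reaches about 74-89%.
- With both paths moderate, taken as 0.5 SD and about 0.7 log-odds per SD, power exceeds 80% for the binary outcome. Moderate paths are the plan's own first assumption.
- Aim 1, not Aim 3, sets the sample size.

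All of this stands, and it rules out three stronger readings that a reader might infer.

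- **That true power is a third.** This needs .2 to be an SD difference, which returns only 28% even in the linear model and so does not fit the plan's own figure. C.13 does code groups as dummies against usual care, and C.12 elsewhere uses SD units, which lends that reading some support. But the coding is stated for Aim 1 and does not settle the scale.
- **That the logistic model causes the low figure.** At 0.2 SD the linear model is just as weak; the scale of .2 drives it.
- **That a null result will be reported as absence of mechanism.** The documents speak only of potential mediators and set no such rule.

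The defence does not show that the stated 80% applies to the analysis in C.13. It holds only for some choices of scale and test, and the plan does not say which it made.

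**Conclusion.** The concern holds as a matter of an unestablished figure. The 80% for Aim 3 cannot be traced to the planned analysis: the path labels conflict, the mediator-to-outcome effect is not given, and the scale and alpha are unstated.

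At the stated values, Sobel power for the binary outcome is below 80% on every reading tried (3-77%). With the planned bootstrap it is about a third or less if .2 is a 0.2 SD difference between arms. It is about 40-90% if .2 is a standardised coefficient, and where it falls in that range depends mainly on the scale of .39. If both paths are truly moderate, 80% is attainable.

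These results assume two-sided .05, .39 as the mediator-to-outcome effect, the planned screening rates and 115 per arm. The documents do not support saying that the 80% has been refuted. The point warrants correction but does not affect Aim 1.

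**What to change.** Replace the Aim 3 power statement in C.12 with power simulated for the planned model: two arms of about 112-115, 0/1 arm, continuous mediator, binary outcome at 5/20/44%, percentile bootstrap. State the intervention-to-mediator effect in SD between arms, the mediator-to-outcome effect as an odds ratio per mediator SD, and the alpha. Delete the wording that gives .39 for the independent variable on the outcome. If the restated power is below 80% at the effect sizes assumed, label Aim 3 exploratory, as Aim 2 already is.

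The cost is a short simulation and a change of protocol wording, and the restated figure may be less favourable. Enrolment should not change, because Aim 1 determines it.
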